#### 4.1.2 Cut-off dates

The cut-off dates for various DBL analyses will be defined as follows:

Week 24 DBL and analysis: For all domains with visit numbers (e.g. LV, VS, EG etc.), Week 24 visit number will be used for cut-off. For event domains without visit numbers (e.g. AE, CM, MH etc.), the date in DS (the disposition date to complete or discontinue Week 24) will be used for cut-off.

Week 52 DBL and analysis: For all domains with visit numbers (e.g. LV, VS, EG etc.), Week 52 visit number will be used for cut-off. For event domains without visit numbers (e.g. AE, CM, MH etc.), the date in DS (the disposition date to complete or discontinue Week 52) will be used for cut-off.

Week 112 / End of Study DBL and analysis: All data up to Day 799 will be included in the end of study analysis..

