X = assessment to be recorded in clinical data base

S = assessment to be recorded on source documentation

* Subjects who prematurely discontinue during Treatment Period 1 should return for assessments associated with Week 24 visit (4 weeks after the last study treatment in Treatment Period 1) and the follow-up visit (Week F112) 12 weeks after the last study treatment. Subjects who prematurely discontinue during Treatment Period 2 should return and complete assessments associated with Week 52 visit (4 weeks after the last study treatment in Treatment Period 2) and the follow-up visit (Week F112) 12 weeks after the last study treatment.

Table 6-2 Assessment schedule - Part 2: Week 56 to Week 104 and Follow-up visit F112

| Week | Treatment period 3 | | | | | | | | | | | | | Follow-up |
|---|--------------------|----|----|----|----|----|----|----|----|----|----|-----|--------------------|---------------------|
| | 56 | 60 | 64 | 68 | 72 | 76 | 80 | 84 | 88 | 92 | 96 | 100 | 104* TD/PS W | |
| Optional site visit ¹ | X | | X | | X | | X | | X | | X | | | |
| Administration of s.c. study treatment via PFS | X | X | X | X | X | X | X | X | X | X | X | X | | |
| Physical Exam | | S | | S | | S | | S | | S | | S | S | S |
| Weight | | | | | X | | | | | | | | X | X |
| Vital signs | X | | X | | X | | X | | X | | X | X | X | |
| ECG | | | | | X | | | | | | | | X | |
| Hematology, blood chemistry, urinalysis | | X | | X | | X | | X | | X | | | X | |
| Urine pregnancy test ² | | X | | X | | X | | X | | X | | | X | |
| Concomitant medication/non- drug therapy | | | | | | | | | | | | | | Update as necessary |
| AE/SAE (including injection site reaction, occurrence of infection) | | | | | | | | | | | | | | Update as necessary |
| ANA | | | | | | | | | | | | | X | |
| Anti-dsDNA | | | | | | | | | | | | | X | |
| | | | | | | | | | | | | | | |
| High sensitivity C-Reactive protein (hsCRP) | | X | | X | | X | | X | | X | | | X | X |
| Erythrocyte Sedimentation Rate (ESR) ² | | X | | X | | X | | X | | X | | | X | X |
| X-ray (hands/wrists + feet) | | | | | | | | | | | | | X ³ | |
| Tender and swollen joint counts (TJC78, SJC76) | | X | | X | | X | | X | | X | | | X | |
| Patient's assessment of PsA pain (VAS) | | X | | X | | X | | X | | X | | | X | |
| Patient's global assessment of disease activity (VAS) | | X | | X | | X | | X | | X | | | X | |
| | | | | | | | | | | | | | | |

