7.2.2 Serious adverse event reporting

To ensure subject safety, every SAE, regardless of causality, occurring after the subject has provided informed consent and until 12 weeks (84 days) after last administered dose of study treatment or 30 days after the subject has stopped study participation (whichever is later) must be reported to Novartis within 24 hours of learning of its occurrence.

Any SAEs experienced after this period should only be reported to Novartis if the investigator suspects a causal relationship to study treatment.

Information about all SAEs is collected and recorded on the Serious Adverse Event Report Form; all applicable sections of the form must be completed in order to provide a clinically thorough report. The investigator must assess the relationship of each SAE to each specific component of study treatment, (if study treatment consists of several components) complete the SAE Report Form in English, and submit the completed form within 24 hours to Novartis. Detailed instructions regarding the submission process and requirements for signature are to be found in the investigator folder provided to each site.

Follow-up information is submitted as instructed in the investigator folder. Each re-occurrence, complication, or progression of the original event must be reported as a follow-up to that event regardless of when it occurs. The follow-up information should describe whether the event has resolved or continues, if and how it was treated, whether the blind was broken or not, and whether the patient continued or withdrew from study participation

If the SAE is not previously documented in the IB or Package Insert (new occurrence) and is thought to be related to the investigational treatment a Drug Safety and Epidemiology Department associate may urgently require further information from the investigator for Health Authority reporting. Novartis may need to issue an Investigator Notification (IN) to inform all investigators involved in any study with the same investigational treatment that this SAE has been reported. Suspected Unexpected Serious Adverse Reactions (SUSARs) will be collected and reported to the competent authorities and relevant ethics committees in accordance with EU Guidance 2011/C 172/01 or as per national regulatory requirements in participating countries.

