9.5.3 Safety variables

Adverse events

Treatment emergent AEs (events that started after the first dose of study treatment or events present prior to the first dose of study treatment but increased in severity based on preferred term) will be summarized up to 12 weeks (84 days) after the last dose.

AEs will be summarized by presenting, for each treatment group, the number and percentage of subjects having any AE, having an AE in each primary system organ class and having each individual AE (preferred term). Summaries will also be presented for AEs by severity and for study treatment related AEs. If a subject reported more than one AE with the same preferred term, the AE with the greatest severity will be presented. If a subject reported more than one AE within the same primary system organ class, the subject will be counted only once with the greatest severity at the system organ class level, where applicable. SAEs will also be summarized.

These summaries may be presented separately by study periods.

As appropriate, the incidence of AEs will be presented per 100 subject years of exposure.

Separate summaries will be provided for death, SAE, other significant AEs leading to discontinuation and AEs leading to dose adjustment (including study treatment discontinuation).

A graphical display of relative frequencies within system organ classes and relative risks, as appropriate, will be presented.

[figure not shown]
When adjudication is required of major cardiovascular events, a summary of those types of events as reported by the investigator and confirmed by adjudication will be provided.

Laboratory data

The summary of laboratory evaluations will be presented for three groups of laboratory tests (hematology, serum chemistry and urinalysis). Descriptive summary statistics for the change from baseline to each study visit will be presented. These descriptive summaries will be presented by test group, laboratory test and treatment group. Change from baseline will only be summarized for subjects with both BSL and post- BSL.

For each parameter, the maximum change from baseline within each study period will be evaluated analogously.

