### **2.8.1 Adverse events (AEs)**

The crude incidence of treatment emergent adverse events (AEs) (i.e. events started after the first dose of study treatment or events present prior to the first dose of study treatment but increased in severity based on preferred term and on or before last dose + 84 days) will be summarized by primary system organ class and preferred term. Confidence intervals for the crude rate will be derived as described in [Section 4.2.4.1](#) In addition, exposure time-adjusted rates (incidence rate) including 95% confidence intervals will be provided for the entire treatment period (see [Section 4.2.5.1](#)) to adjust for differences in exposure. Graphical displays of the crude incidence rates and exposure-adjusted rates will be presented for all AEs and serious AEs by system organ class.

Adverse events reported will be presented in descending frequency according to its incidence in total secukinumab group (combining all secukinumab treatment groups) starting from the most common event. Summaries (crude incidences only) will also be presented for AEs by severity and for study treatment related AEs. If a particular AE 'severity' is missing, this variable will be listed as missing and treated as missing in summaries. If a subject reported more than one adverse event with the same preferred term, the adverse event with the greatest severity will be presented. If a subject reported more than one adverse event within the same primary system organ class, the subject will be counted only once with the greatest severity at the system organ class level, where applicable.

Separate summaries will be provided for adverse events suspected to be related to study drug, deaths, serious adverse events, and adverse events leading to discontinuation and adverse events leading to temporary dose interruption.

Adverse events will also be reported separately by SMQ according to MedDRA. The MedDRA version used for reporting the study will be described in a footnote.

Non-treatment emergent adverse events will be listed.

Algorithms for date imputations will be provided in RAP M8.

For serious adverse events (SAEs) occurred during screening a listing will be prepared for all subjects screened including screening failures.

When adjudication is required of major cardiovascular events, a listing of those types of events as reported by the investigator and confirmed by adjudication will be provided.

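### SAP 4.1.2 cuts a discontinuer's adverse events at the period disposition date, which probably defers most of the 84-day treatment-emergent window from the interim analyses to the final one

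*SAP*

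**What the plan says.** **Cut-off.** SAP 4.1.2 sets one rule per lock for event domains without visit numbers (AE, CM, MH). At Week 24, "the date in DS (the disposition date to complete or discontinue Week 24) will be used for cut-off". At Week 52, "the date in DS (the disposition date to complete or discontinue Week 52) will be used for cut-off". Visit-based domains are cut at the Week 24 or Week 52 visit number. Only the last lock differs: "All data up to Day 799 will be included in the end of study analysis".

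**Treatment-emergent window.** SAP 2.8.1 counts events that started after the first dose, or were present before it "increased in severity based on preferred term and on or before last dose + 84 days". Protocol 9.5.3 says that treatment-emergent events "will be summarized up to 12 weeks (84 days) after the last dose". SAP 2.8 says that the entire-treatment-period summary includes follow-up.

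**Collection.** Protocol 7.2.2 requires SAE reporting "until 12 weeks (84 days) after last administered dose of study treatment or 30 days after the subject has stopped study participation", whichever is later. The footnote to protocol Table 6-1 reads "Subjects who prematurely discontinue during Treatment Period 1 should return for assessments associated with Week 24 visit (4 weeks after the last study treatment" in that period, and adds a follow-up visit (F112) at 12 weeks after the last treatment. Protocol 5.5.9 says the same.

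**The concern.** For a subject who completes the period and stays on treatment, the rule is an ordinary data cut. For a subject who has stopped, it ends observation well before the window that the same SAP uses to define a treatment-emergent event. Events in the gap have been collected, and they may fall before calendar Week 16, 24 or 52, yet they do not enter that lock's tables. The subject still counts in the crude-incidence denominator.

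The shortened observation applies only to people who stopped early. Adverse events, laboratory abnormalities and worsening are among the reasons for stopping in protocol 5.5.9. SAP 2.8 relies on the period up to rescue for its placebo comparison. SAP 2.13 plans the Week 52 analysis for submission and/or publication, and protocol 5.4 allows Week 24 summary results to be shared externally. A table for one fixed period, such as Day 1 to Week 16, could therefore show different counts at an interim lock and at the final lock if it is produced at both.

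**Working it through.** **1. The plan's own figure.** 12 weeks × 7 = 84 days, as stated.

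**2. Where the disposition date falls.** The documents do not say which date fills the DS domain, so it has to be inferred.
- The Treatment Period 1 and 2 completion forms are scheduled at the end-of-period visits (Table 6-1).
- A discontinuer attends that visit 4 weeks, or 28 days, after the last treatment.
- Follow-up has its own completion form (Table 6-2), so a date tied to completing or discontinuing Week 24 or Week 52 points to the period form.
- The date is therefore most likely 28 days after the last dose or earlier.

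**3. Share of the window omitted.** Omitted share = (84 − k)/84, where k is the number of days from last dose to disposition.

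| k | Days omitted | Share |
|---|---|---|
| 28 | 56 | 66.7% |
| 14 | 70 | 83.3% |
| 0 | 84 | 100% |

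The omitted part falls to half only at k = 42, which the 4-week visit does not foresee.

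**4. Example.** Last dose at Week 4 (Day 29), end-of-period visit on Day 29 + 28 = Day 57, SAE on Day 78.
- 78 − 29 = 49 days after the last dose, which is under 84, so the event is treatment-emergent.
- Week 16 is Day 16 × 7 + 1 = 113, so the event lies inside Day 1 to Week 16.
- Day 78 is after Day 57, so the event is cut from the Week 24 lock.
- At the Week 52 lock the answer is unclear. A subject who left in Period 1 has no evident Period 2 disposition date, so the rule could mean the Period 1 date or no cut.
- A full 84-day window fits before Week 16 only if the last dose was by Day 113 − 84 = Day 29.

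**5. Size at the Week 52 lock.** Protocol section 4 gives about 990 subjects and 25% first-year dropout.
- Discontinuers: 0.25 × 990 = 247.5.
- Omitted follow-up: 247.5 × 56/365.25 = 37.9 subject-years.
- First-year exposure, assuming last doses spread evenly over 48 weeks (mean 24 weeks) and each discontinuer followed for 84 days: (742.5 × 364 + 247.5 × (168 + 84))/365.25 = 910.7 subject-years.
- Share: 37.9/910.7 = 4.2%.
- Same method at 10% dropout: 15.2 subject-years (1.6%). At 5%: 7.6 (0.8%).
- If Period 1 discontinuers are not cut at Week 52, even spread puts half of the dropouts (24 of 48 weeks) outside the rule: 37.9 × 0.5, about 19 subject-years.

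**6. Exposure.** SAP 2.4.1 ends exposure, for subjects who do not switch, at the earlier of last dose + 84 days and the last visit date. If F112 counts as the last visit at an interim lock, the denominator includes up to 56 days in which events were cut. If visits are also cut at the Week 24 or Week 52 visit, numerator and denominator stop at about the same point.

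**The case against.** The strongest case on the other side is that this is a missing definition. Nothing fixes the DS date, so 28 days is an inference. That stands as a limit on precision. It does not remove the conflict, because the separate period and follow-up forms place the date at or before the 4-week visit, and an earlier date omits more.

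Several stronger readings are tempting, and the documents do not support them.
- **That events are lost.** They are deferred: the final analysis takes data to Day 799, and SAEs reach the sponsor within 24 hours regardless.
- **That a Period 1 discontinuer's late events are missing from the Week 52 tables.** The rule is ambiguous for these subjects.
- **That the comparison between arms is biased.** This would need different dropout or event timing by arm. The documents give neither, so uneven loss is possible but not shown.
- **That exposure-adjusted rates are wrong.** They may already be coherent, depending on how the last visit date is cut.
- **That both interim analyses are for submission or publication.** This purpose is stated for Week 52 only, and protocol 9.6 says only that those analyses may be so used.

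The size is also open to challenge. The 38 subject-years assume that every discontinuer supplies a full window before the lock. After withdrawal of consent no further assessments are made (protocol 5.5.10), and subjects lost to follow-up may supply nothing.

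Finally, simply extending discontinuers to last dose + 84 days would create a new asymmetry. A last dose on Day 141 would be followed to Day 225, while completers are cut near Day 169. This stands, and the remedy has to cap for it.

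**Conclusion.** The point holds as an inconsistency between the interim cut-off and the SAP's own treatment-emergent definition. For a discontinuer, about 56 of 84 days or more are omitted from the interim analysis of the period in which the subject stopped. This rests on the disposition being dated no later than the end-of-period visit. The clear effect is that crude incidence is understated at the interim locks, because these subjects remain in the denominator.

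The overall size is modest. About 38 subject-years, or 4% of first-year exposure, is a loose upper bound at 25% dropout. It assumes complete 84-day follow-up before the lock and that Period 1 discontinuers are also cut at Week 52. The effect on the Day 1 to Week 16 table cannot be sized from the documents. Primary efficacy is untouched. The change is worth making because the omission falls only on subjects who stopped early and is cheap to avoid.

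**What to change.** In SAP 4.1.2:
- Keep the disposition date as the AE/CM cut-off for subjects who complete the period.
- For subjects who discontinue, use the earliest of last dose + 84 days, the nominal end of the period (Week 24 = Day 169; Week 52 = 52 × 7 + 1 = Day 365) and last contact before the lock. The nominal cap keeps discontinuers from being followed longer than completers.
- State that at the Week 52 lock this also applies to subjects who discontinued in Period 1.
- End exposure in SAP 2.4.1 on the same date.

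In the example, the cut-off becomes Day 113 (29 + 84), so the Day 78 event is kept at Week 24. For a last dose on Day 141 the cap gives Day 169, which is the 4-week visit itself, so nothing changes. A full window is kept at Week 24 for last doses up to Day 85 (169 − 84) and at Week 52 up to Day 281 (365 − 84).

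The cost is SAP wording, one extra programming rule and slightly higher reported event counts. No new collection is needed for subjects who attend follow-up or whose SAEs are reported; those who withdrew consent or were lost may add little.

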### 4.2 Detailed on implementation of statistical methodology and assumptions

#### 4.2.1 Analysis of continuous data

##### 4.2.1.1 Summary statistics for continuous data

Summary statistics (including N, mean, standard deviation, minimum, lower quartile, median, upper quartile, maximum) will be provided for continuous data by visit and treatment group.

##### 4.2.1.2 Mixed-effects repeated measures model

Endpoints with continuous data type expected to be normally distributed (e.g, DAS28) will be analyzed using a mixed-effects repeated measures model (MMRM) with treatment, stratification factor and analysis visit as factors; and weight, baseline value, treatment by visit and baseline by visit interactions as covariates. An unstructured covariance structure will be assumed for this model. The significance of the treatment effects for secukinumab regimens at different analysis visits will be determined from the pairwise comparisons performed between secukinumab regimens and placebo at the appropriate analysis visits.

SAS code for mixed model:

```
proc mixed data=aaa;
class TRT USUBJID AVISITN STRATA;
model CHG=TRT STRATA AVISITN WEIGHT BASE TRT*AVISITN BASE*AVISITN
/ s ddfm=kr;
lsmeans TRT*AVISITN / diff cl;
repeated AVISITN / type=un subject=USUBJID;
Run;
```

In case the MMRM model does not converge the following sequential steps will be used:

1. change ddfm=kr to ddfm=bw. If still no convergence, perform step 2.
2. change type=un to type=cs. If still no convergence, perform step 3.
3. remove covariates in the following order until convergence: WEIGHT, BASE\*AVISITN, STRATA.

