### **Physical function (HAQ-DI©)**

Between-treatment differences in the change in HAQ-DI© will be evaluated using a MMRM with treatment, analysis visit and TNF-alpha inhibitor status as factors, and weight and BSL HAQ-DI© score as continuous covariates. Treatment by analysis visit and BSL by analysis visit will be included as interaction terms in the model. An unstructured covariance structure will be assumed for this model. The significance of the treatment effects for secukinumab regimens at different analysis visits will be determined from the pairwise comparisons performed between secukinumab regimens and placebo at the appropriate analysis visits.

The primary estimand for HAQ-DI is the estimated treatment differences (each secukinumab dose vs. placebo) at week 16 in the FAS population applying the MMRM model described above under the MAR assumption for any missing data.

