## **Changes in DAS28-CRP**

Between-treatment differences in the change from baseline in DAS28-CRP will be compared by means of a MMRM with treatment regimen, analysis visit, and TNF-alpha inhibitor status as factors, and weight and BSL as continuous covariates. Treatment by analysis visit and BSL by analysis visit will be included as interaction terms in the model. An unstructured covariance structure will be assumed for this model. The significance of the treatment effects for secukinumab regimens at different analysis visits will be determined from the pairwise comparisons performed between secukinumab regimens and placebo at the appropriate analysis visits.

The primary estimand for DAS28-CRP is the estimated treatment differences (each secukinumab dose vs. placebo) at week 16 in the FAS population applying the MMRM model described above under the MAR assumption for any missing data.

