## **3 Sample size calculation**

A 5% two-sided type I error rate will be used to control for type I error. Three secukinumab regimens will be tested versus placebo with respect to the primary endpoint (ACR20 response at Week 24), thus the type-I-error will be split to 1.67% two-sided for each comparison. Sample sizes will be based on this type I error assumption. With an assumed placebo rate of 15% and secukinumab 51% (FUTURE 2), the study is over 99% powered to detect a treatment difference of ACR20 in the FAS population, assuming 220 subjects in a secukinumab treatment group, and 330 subjects in the placebo group (Fisher's exact test, nQuery 7.0). This power is applicable for all three dose regimens, as the sample size is driven by structural endpoint.

Power for secondary variables was calculated using a two-sided 1.67% type I error. With an assumed placebo rate of 7% and secukinumab 35% (FUTURE 2), the study is over 99% powered to detect a treatment difference of ACR50 in the full FAS population, assuming 220 subjects in a secukinumab treatment group, and 330 subjects in the placebo group (Fisher's exact test, nQuery 7.0).

For structural endpoint, historical data (FUTURE 1) showed a standard deviation of 1.132 on active treatment and 2.435 on placebo at Week 24, and a difference of 0.52. Using the above assumptions, there is 83% power to show statistically significant differences assuming 220 subjects in a secukinumab group and 330 subjects in the placebo group (Satterthwaite t-test, nQuery 7.0).

A standard deviation of approximately 0.49 and a treatment difference of 0.17 has been observed for the change from baseline at Week 24 in HAQ-DI® (FUTURE 2). Using those assumptions, the study has approximately 94% power to detect a difference between secukinumab and placebo (Two group t-test, nQuery Advisor 7.0), assuming 220 subjects in a secukinumab treatment group and 330 subjects in the placebo group.

For the presence of dactylitis at Week 24 in the subset of subject who have dactylitis at BSL, with an assumed placebo rate of 85% and secukinumab 50% (FUTURE 2), there is about 99% power to show statistically significant difference between secukinumab (110) and placebo (165 subjects), assuming 50% subject have dactylitis at BSL (Fisher's exact test, nQuery 7.0).

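### If the unstructured MMRM fails to converge, the SAP falls back to compound symmetry with model-based standard errors, which can misstate the Week 16 variance for HAQ-DI and DAS28-CRP (minor)

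*SAP*

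**What the plan says.** For HAQ-DI and DAS28-CRP, SAP 2.6.2.2 specifies an MMRM with treatment, visit, TNF status, weight, baseline, and the treatment-by-visit and baseline-by-visit interactions. On the covariance it says: "An unstructured covariance structure will be assumed for this model". Both endpoints are read off at one visit: "The primary estimand for HAQ-DI is the estimated treatment differences (each secukinumab dose vs. placebo) at week 16 in the FAS population", and likewise "The primary estimand for DAS28-CRP is the estimated treatment differences (each secukinumab dose vs. placebo) at week 16 in the FAS population". They are H16 to H21 in the family-wise testing procedure (SAP 2.6.2.1).

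SAP 4.2.1.2 gives the code and a fallback: "In case the MMRM model does not converge the following sequential steps will be used". The steps are:

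1. The degrees-of-freedom method goes from Kenward-Roger to between-within, with the covariance left unstructured.
2. For the covariance, the instruction is: "change type=un to type=cs. If still no convergence, perform step 3".
3. Weight, then baseline-by-visit, then the stratum are taken out until the model converges.

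The code opens with "proc mixed data=aaa" and has no EMPIRICAL option. None of the three steps adds one.

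**The concern.** An unstructured matrix gives Week 16 its own variance. Compound symmetry replaces all visit variances with one pooled value and all correlations with one common value. With model-based standard errors, the Week 16 contrast is then judged against the pooled variance. If Week 16 is more variable than the average modelled visit, the standard error is too small and the test rejects too often. If it is less variable, the test is conservative.

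Four of the seven scheduled visits up to Week 16 fall in Weeks 1 to 4 (Protocol Table 6-1), so early visits weigh heavily in the pool. At stake is the calibration of six confirmatory tests in the one situation where the fallback is used. Step 3 can also remove TNF status, on which randomisation was stratified.

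**Working it through.** **Inputs from the documents.** Group sizes are 220 per secukinumab regimen and 330 on placebo. HAQ-DI: difference 0.17, SD 0.49. DAS28-CRP: difference 0.62, SD 1.04 (all SAP 3). Joint counts, patient global, hsCRP and HAQ-DI are scheduled at Weeks 1, 2, 3, 4, 8, 12, 16, 20 and 24 (Protocol Table 6-1). First-year dropout is 25% (Protocol 4), about 25% × 16/52 = 7.7% by Week 16.

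**The plan's own figure.** SAP 3 states "Power for secondary variables was calculated using a two-sided 1.67% type I error" and about 94% power for HAQ-DI. The standard error is 0.49 × √(1/220 + 1/330) = 0.0426, so the expected z is 0.17/0.0426 = 3.99. The two-sided 1.67% critical value is 2.394, and Φ(3.99 − 2.394) = 94.4%. The stated power is reproduced. It does not depend on the fallback.

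**Assumption.** No SD by visit is given. Set the Week 16 SD to 1 and let the SD move linearly in log(week) from r at Week 1 to 1 at Week 16. After Week 16 it either continues on that line or stays flat.

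**Formulas.** With complete data and a full treatment-by-visit mean, the compound-symmetry fit leaves the Week 16 mean difference unchanged. Only its standard error changes:

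- SE ratio = √(mean visit variance ÷ Week 16 variance)
- true type I error = 2 × [1 − Φ(1.96 × SE ratio)]

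**Worked example (r = 0.8, seven visits).** The SDs are 0.800, 0.850, 0.879, 0.900, 0.950, 0.979 and 1.000. The mean of their squares is 0.830, the SE ratio is 0.911, and the type I error is 2 × [1 − Φ(1.785)] = 7.4%.

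| r = SD(Week 1)/SD(Week 16) | Visits to Week 16 | To Week 24, SD continues | To Week 24, SD flat after Week 16 |
|---|---|---|---|
| 1.2 | 3.2% | 3.6% | 3.5% |
| 1.0 | 5.0% | 5.0% | 5.0% |
| 0.8 | 7.4% | 6.6% | 6.8% |
| 0.6 | 10.5% | 8.4% | 8.9% |
| 0.5 | 12.2% | 9.4% | 10.0% |

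**Simulation check.** Four groups (330/220/220/220), visits to Week 16, correlation 0.85 between adjacent visits, 8% dropout by Week 16 unrelated to outcome, no baseline covariates, 1,500 runs per row. The Monte Carlo margin near 5% is ±1.1 points.

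| r | Compound symmetry, model-based SE | Compound symmetry, sandwich SE |
|---|---|---|
| 1.2 | 3.7% | 5.1% |
| 1.0 | 5.3% | 5.2% |
| 0.8 | 7.3% | 4.9% |
| 0.6 | 10.7% | 5.9% |

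With adjacent-visit correlation 0.7 and r = 0.6, the two columns read 10.8% and 5.1%. The formula holds up under modest dropout, and the sandwich estimator brings the error back to about 5%.

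**The case against.** The best reply is that this is remote and its direction unproven. Much of that stands.

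- **Trigger.** Nothing in the documents suggests that the unstructured model will fail, and with about 990 subjects and seven to nine visits it should fit.
- **Gatekeeping.** H16 is reached only after H1 to H6, H7, H10 and H13 are rejected. The two 150 mg regimens come later still.
- **Planning effects.** Expected z is 3.99 for HAQ-DI and 0.62/0.0905 = 6.85 for DAS28-CRP. At the 5% level, even an SE ratio of 0.79 only moves HAQ-DI rejection from 97.9% to 99.3%, so a wrong conclusion is unlikely if those effects are real.
- **Model.** The SD that matters is the residual SD after adjusting for baseline by visit, weight and stratum. The calculation uses the raw SD of change, so r is a stand-in.
- **Visit set.** The SAP does not say which visits enter the model. A model to Week 52 with SD still rising would be close to nominal. However, SAP 4.1.2 cuts the data for the primary analysis at the Week 24 visit, so nine visits is the natural maximum. SAP 2.6.3 also sets placebo data after the Week 16 switch to missing, which shifts the pool towards earlier visits.

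A pre-specified, ordered fallback is good practice, and several ladders would be acceptable. What remains is that the one chosen is calibrated only if the Week 16 variance happens to equal the visit average.

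**Conclusion.** The point holds as a conditional, minor one. After non-convergence, the Week 16 tests of HAQ-DI and DAS28-CRP would use a pooled variance with no protection against unequal visit variances. At nominal 5%, for r from 0.8 to 0.5, true type I error is about 6.6–10.0% with visits to Week 24 and 7.4–12.2% if the model stops at Week 16. It is 5.0% at r = 1.0 and about 3.2–3.6% at r = 1.2. These figures rest on the assumed log-linear SD profile and on complete data. The unstructured analysis and the stated power are unaffected.

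A reader might infer more than the documents support:

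- **That compound symmetry necessarily understates the Week 16 variance.** No SD by visit is given, and equal or falling SDs give nominal or conservative tests.
- **That the 1.67% level applies.** SAP 3 uses it for power; SAP 2.6.2.1 tests the second family at full alpha.
- **That baseline may be dropped.** Step 3 can remove the baseline-by-visit interaction, but the baseline main effect is not on the list.
- **That step 1 does harm.** It leaves the unstructured matrix in place. It would rarely cure non-convergence, but keeping it introduces no error.

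**What to change.** In SAP 4.2.1.2:

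- **Step 2.** For any structure other than unstructured, use empirical (sandwich) standard errors with between-within degrees of freedom. The latter are already in force after step 1.
- **Step 2, preferably also.** Before compound symmetry, try heterogeneous structures in a fixed order, for example heterogeneous Toeplitz, heterogeneous AR(1), then heterogeneous compound symmetry. This lets the variance differ by visit in the model itself, whereas the sandwich corrects only the standard error.
- **Step 3.** Keep STRATA in the model, since it is the randomisation factor.
- **Visits.** State which visits enter the Week 16 model.

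The cost is a few lines of SAP text and code. The downside is slightly lower efficiency if a simple structure is in fact true.
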